8.2.3 Collection and Recording of Adverse Events for Maternal Subjects

Events that occur in maternal subjects following the signing of informed consent are to be collected as AEs. Data regarding these AEs are to be recorded in the e-CRF. Maternal subject AEs will be collected and recorded from the time of signing ICF through the Day 18/Follow-up visit.

8.2.4 Collection and Recording of Adverse Events for Infants

Events that occur in infants following the signing of parental consent are to be collected as AEs. Data regarding these AEs are to be recorded in the e-CRF using information obtained from the infant's hospital records (as available). Infant AEs will be collected and recorded from the time informed consent is obtained through the Day 18/Follow-up visit during the trial. As part of post-trial activities after the Day18/Follow-up visit, infant AEs will also be collected and recorded through time of infant's discharge from NICU or until the last milk sample expressed during maternal subject's treatment with IMP is either consumed by the infant or discarded, whichever occurs last. These AEs will be reported separately from those collected through the Day 18/Follow-up visit.

About one month after the infant's NICU discharge, the maternal subject will be contacted (by phone or other means) to inquire about any hospital re-admission and the reason for such.

8.3 Adverse Events Requiring Special Handling for Maternal Subject

8.3.1 Uterine Contraction

As uterine contraction during postpartum is considered a physiological phenomenon, uterine contraction is not to be reported as AEs unless it requires active management, e.g., analgesic use.

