1.3 Benefit/Risk Aspects

The present trial will be the first to provide efficacy data in the target population. As a proof of concept (PoC) trial, the primary purpose is to test the hypothesis that exposure to merotocin results in increased milk production in women with preterm delivery and inadequate milk production.

A double electric breast pump will be provided to all maternal subjects entering the observation period. Maternal subjects will receive lactation counselling comprised of best supportive care for this population at trial entry and ongoing support throughout the trial. This is an important benefit of participation because postnatal lactation support is associated with increased rates of breastfeeding and improved infant outcomes.^{20,21}

A potential benefit of the trial in general is identification of a pharmacologic intervention that will increase the maternal subjects' ability to produce an adequate amount of MoM to meet their infants' nutritional needs. There are known clinical benefits to premature infants receiving human milk, including shorter time to tolerance of full enteral feedings^{3,12,13} and reduced risk of NEC,^{2,3,4,5} ROP,⁶ sepsis,^{7,8} BPD^{9,10,11} and respiratory distress syndrome (RDS)²².

The risk profile to date is described in the Investigator's Brochure.¹⁹ Merotocin has previously been given to healthy women without any significant undesirable effects. During the single ascending dose and multiple ascending dose trial in healthy women, the most frequently reported adverse events (AEs) were headache, dry mouth, and flushing (hot flush). In that trial, an increased heart rate was observed following a constant rate intravenous infusion which gave rise to high plasma concentrations. During the other phase 1 trial that investigated the transfer of merotocin from blood to breast milk in healthy women, the most frequently reported AEs were uterine spasm, breast engorgement, and headache.

Other effects associated with the pharmacological activity that is possibly mediated by the oxytocin receptor may occur. As such, undesirable effects reported for oxytocin following rapid intravenous bolus and intravenous infusions include cardiac arrhythmia, hypotension, bradycardia, and hypersensitivity.

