2 TRIAL OBJECTIVES AND ENDPOINTS

2.1 Objectives

Primary Objective

- To evaluate the effect of merotocin on increasing milk production in women with preterm delivery and with inadequate milk production

Secondary Objectives

- To evaluate the effect of merotocin on milk production after treatment discontinuation
- To evaluate the amount of mother's own milk (MoM) in the infant enteral nutritional intake and changes in infant body weight
- To evaluate any amount of merotocin from maternal plasma into the milk expressed by women with preterm delivery exposed to merotocin
- To characterize the safety profile of merotocin in women with preterm delivery and their infants

Exploratory Objectives

- To explore the relationship between merotocin exposure in maternal plasma and milk volume
- To evaluate composition of milk produced during treatment with merotocin in women with preterm delivery

Post-trial Objectives

- To explore post-trial feeding patterns and key parameters of neonatal intensive care unit (NICU) hospitalization of infants from women with preterm delivery and inadequate milk production
- To assess the post-trial long-term development of infants from women with preterm delivery and inadequate milk production

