2.2 Endpoints

Primary Endpoint

- Volume of MoM produced over Days 1 to 14

Secondary Endpoints

- Time to the first occurrence of a daily volume of MoM ≥ 500 mL and ≥ 750 mL

- Proportion of maternal subjects with a daily volume of MoM ≥ 500 mL and ≥ 750 mL over Days 1 to 14
- Volume of MoM produced over Days 15 to 17 (after treatment discontinuation)
- Volume of MoM fed to the infant over Days 1 to 14
- Volume of formula/donor milk fed to the infant over Days 1 to 14
- Merotocin concentration in milk produced at Day 3 and Day 10 visits
- Changes in infant body weight over Days 1 to 14
- Frequency and intensity of AEs in maternal subjects
- Frequency and intensity of AEs in infants
- Changes in routine safety laboratory parameters in maternal subjects and proportion of subjects with markedly abnormal changes at Day 15/End-of-Treatment visit

Exploratory Endpoints

- Merotocin concentration in maternal plasma at Day 3 and Day 10 visits
- Composition of milk (including lipids, protein, caloric content, lactose, and Human Milk Oligosaccharides) produced by maternal subjects at Day 3 and Day 10 visits

Post-trial Endpoints

[figure not shown]
- Time to tolerance of full (150 mL/kg/day) enteral feed of the infant
- Time to NICU discharge of the infant
- Number of days the infant requires total parenteral nutrition (TPN) until time of discharge from NICU
- Proportion of maternal subjects who are lactating at time of infant's discharge from NICU
- Proportion of infants who are fed with MoM/formula/donor milk at time of discharge from NICU
- Body weight, length, and head circumference of the infant at time of discharge from NICU
- Incidence of infant's morbidity events of special interest (including necrotizing enterocolitis (NEC), intra-ventricular hemorrhage, bronchopulmonary dysplasia (BPD), respiratory distress syndrome (RDS), late-onset sepsis, ROP, and hemodynamically significant patent *ductus arteriosus*) until time of discharge from NICU
- Proportion of infants with an Ages and Stages Questionnaire-3 (ASQ-3) score in the black zone in any domain at 9 months, 18 months and 24 months of corrected gestational age

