3.6.5 Selection and Timing of Dose for Each Subject

Following intra-nasal administration of merotocin, the time to maximum observed concentration (t_{max}) and $t_{1/2}$ are approximately 12 to 15 minutes and 25 to 35 minutes, respectively.¹⁹ In the phase 1 milk transfer trial, pharmacodynamic effect of merotocin in the form of uterine contractions were observed within 5 to 10 minutes after an intravenous dose equivalent to 400 µg intra-nasally. Therefore, the treatment for the maternal subject is administered intra-nasally as 1 spray in each nostril approximately 5 to 10 minutes before each milk expression session.

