8 ADVERSE EVENTS

8.1 Adverse Event Definition

An AE is any untoward medical occurrence in a subject participating in a clinical trial. It includes:

- Any unfavorable and unintended sign, symptom or disease temporally associated with the use of the IMP, whether or not considered to be caused by the IMP
- AEs commonly observed and AEs anticipated based on the pharmacological effect of the IMP
- Any laboratory abnormality, vital sign or finding from physical examination assessed as clinically significant by the investigator [note: findings from assessments and examinations done during screening are not AEs but are recorded as medical history]
- Accidental injuries, reasons for any change in medication (drug and/or dose), reasons for any medical, nursing or pharmacy consultation or reasons for admission to hospital or surgical procedures

Overdoses, medication errors and technical malfunctions of IMP will be captured by the e-CRF and will be reviewed by Ferring Pharmacovigilance on an ongoing basis.

Pre-treatment Adverse Event for Maternal Subjects

A pre-treatment AE for a maternal subject is any untoward medical occurrence arising or observed between informed consent and administration of the IMP.

Treatment-emergent Adverse Event for Maternal Subjects

A TEAE for a maternal subject is any AE occurring after start of the IMP and before the Day 15/End-of-Treatment visit. A pre-treatment AE or pre-existing medical condition that worsens in intensity after start of IMP and before the Day 15/End-of-Treatment visit is also considered treatment emergent.

Pre-treatment Adverse Event for Infants

A pre-treatment AE for an infant is any untoward medical occurrence arising or observed between the signing of the parental informed consent and the infant's first exposure to MoM expressed during maternal subject's treatment period.

Treatment-emergent Adverse Event for Infants

A TEAE for an infant is any AE occurring from the infant's first exposure to MoM expressed during maternal subject's treatment period until the infant's last exposure to MoM expressed during maternal subject's treatment period (i.e., the last milk sample expressed during maternal subject's treatment with IMP is either consumed by the infant or discarded). A pre-treatment AE or pre-existing medical condition that worsens in intensity during the interval stated above is also considered treatment emergent.

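### Section 8.3.1 leaves uterine contractions that need no active management out of AE reporting, so the total frequency and full intensity distribution of this on-target effect cannot be estimated

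*Combined protocol and SAP*

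**What the plan says.** Section 8.3.1 gives a reason and a rule. The reason is: "As uterine contraction during postpartum is considered a physiological phenomenon". The rule is that "uterine contraction is not to be reported as AEs unless it requires active management, e.g., analgesic use". Analgesic use is the only example of active management. The section does not define the term, and it does not say whether spasm or cramping counts as contraction.

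Other sections bear on the same events:

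- Section 8.1 includes among AEs "AEs commonly observed and AEs anticipated based on the pharmacological effect of the IMP".
- Section 3.6.5 reports from the phase 1 milk transfer trial that "pharmacodynamic effect of merotocin in the form of uterine contractions were observed within 5 to 10 minutes after an intravenous dose", a dose it treats as equivalent to 400 µg intra-nasally.
- Section 1.3 says of that trial that "the most frequently reported AEs were uterine spasm, breast engorgement, and headache".
- Section 2.1 sets a secondary objective: "To characterize the safety profile of merotocin in women with preterm delivery and their infants". The matching maternal endpoint in Section 2.2 is "Frequency and intensity of AEs in maternal subjects".
- Sections 9.6.3 and 9.8.2 plan maternal TEAE tables by arm, including by intensity and by causality.

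**The concern.** The plan tells sites not to report part of an effect that it attributes to the drug. Two features make this matter.

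First, the filter does not match the endpoint. The endpoint is frequency and intensity, but the filter is whether the event was managed. Section 8.2.2 grades an event as mild when the woman merely notices it and as moderate when it affects her usual activity. A moderate contraction that she puts up with is therefore not reported. Section 8.3.1 applies no such filter to headache or breast engorgement, the other two events named with uterine spasm in Section 1.3.

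Second, the stated reason does not require the loss. Physiological contraction after delivery occurs in both arms, and a blinded placebo arm is the means of accounting for that background.

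At stake is the description of this effect under 14 days of repeated dosing in postpartum women. Section 1.3 says that this is the first merotocin exposure beyond 45 hours, and the one postpartum phase 1 trial that the protocol describes was single-dose (Section 1.2).

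**Working it through.** There is no figure of the plan's own to reproduce: the protocol gives no contraction rate and no power for any safety comparison. The check compares the sections with each other and then illustrates the size on assumed rates.

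**1. What is recorded, by intensity (Sections 8.2.2 and 8.3.1)**

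| Contraction | Managed | Not managed |
|---|---|---|
| Mild | AE | not reported |
| Moderate | AE | not reported |
| Severe | AE | not reported (probably rare) |

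The left column can be compared between arms. The total over both columns cannot be obtained from the AE data.

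**2. Does another section recover the right column?**

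- Section 7.2.8 plans one targeted search of TEAE terms, for nasal tolerability. There is none for uterine events.
- Section 8.2.1 relies on a general health question and spontaneous reports. There is no solicited uterine item, and an answer that mentions contraction still passes through Section 8.3.1.
- Section 4.3.1 logs medications with their reason, which finds only events that were medicated.
- Section 9.2 summarises reasons for discontinuation, which could show a woman who stopped because of contractions but not one who carried on.
- Section 3.5 has the Safety Committee review AEs, so it sees the same filtered data.

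None of these collects unmanaged contractions systematically.

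**3. Illustration of size**

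Inputs from the protocol: about 100 women randomised 1:1 (Sections 3.2 and 3.1.2), so n = 50 per arm, and a two-sided 5% level (Section 9.6.1). Assumptions, not from the protocol: true contraction rates p0 (placebo) and p1 (merotocin), and a share f of events that are managed, equal in both arms.

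The recorded rate is f × p, so the recorded difference is f × (p1 − p0) and the recorded ratio stays at p1/p0.

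For p0 = 30% and p1 = 60%:

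- f = 1: 50 × 0.30 = 15 v 50 × 0.60 = 30 women; difference 30 points.
- f = 0.5: 7.5 v 15 women expected (15% v 30%); 15 points.
- f = 0.25: 3.75 v 7.5 women expected (7.5% v 15%); 7.5 points.
- f = 0.2: 3 v 6 women (6% v 12%); 6 points.

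The ratio is 2.0 throughout. To show how visible such differences would be, the usual normal approximation for two proportions was used, with a and b the recorded rates and m their mean:

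power = Φ{ [ |b − a| − 1.96 √(2m(1 − m)/n) ] / √[ (a(1 − a) + b(1 − b))/n ] }

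For 30% v 60% with f = 1: m = 0.45; the two standard errors are √(2 × 0.45 × 0.55/50) = 0.0995 and √[(0.30 × 0.70 + 0.60 × 0.40)/50] = 0.0949; (0.30 − 1.96 × 0.0995)/0.0949 = 1.11; Φ(1.11) = 0.87.

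| Assumed true rates, placebo v merotocin | f = 1 | f = 0.5 | f = 0.25 |
|---|---|---|---|
| 10% v 30% | 20 points, power 71% | 10 points, 38% | 5 points, 21% |
| 10% v 40% | 30 points, 95% | 15 points, 62% | 7.5 points, 34% |
| 20% v 50% | 30 points, 89% | 15 points, 51% | 7.5 points, 26% |
| 30% v 60% | 30 points, 87% | 15 points, 43% | 7.5 points, 22% |

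The approximation is rough where few events are expected. The plan sets out no formal test of AEs, so these powers only gauge how clearly a difference would show.

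**The case against.** **The rule is deliberate, disclosed and the same in both arms.** It states its reason and applies under blinding. This stands. A reader might infer that the rule biases the comparison, for example through differing background analgesic use. The documents give no ground for expecting that to differ by arm. What is shown is under-counting and lost information.

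**Sections 8.1 and 8.3.1 need not conflict.** Section 8.1 starts from untoward occurrences, and a sponsor may hold that an unmanaged postpartum contraction is not untoward; a specific rule can qualify a general one. This stands in part: it is a tension and not a flat contradiction. But a contraction that affects usual activity is hard to set aside as merely physiological, and the rule exempts it if it is left unmanaged.

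**The safety objective is still served.** A reader might infer that the maternal safety objective cannot be answered, or that no placebo-controlled comparison of contraction remains. Neither follows. Managed contractions are recorded with intensity and causality and compared with placebo, and all other maternal AEs are unaffected.

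**Contraction may not be the leading reaction.** A reader might infer that it is the most expected effect of the drug. That is an inference. Uterine spasm comes first in a list that is not said to be ranked, from a single-dose intravenous trial after full-term delivery. The other phase 1 trial, which included repeated intra-nasal dosing, lists headache, dry mouth and flushing. That trial, however, enrolled non-lactating women, so it says little about the postpartum uterus.

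**Site examples go beyond the text.** A reader might infer that a woman with cramping after every dose has no AE, or that one already taking analgesics has none because nothing new is given. Section 8.3.1 names contraction, not spasm or cramping, and does not speak of new management. Both readings are possible and neither is settled. The criticism that stands is that the terms are undefined, so sites may classify differently.

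**Conclusion.** The point holds in a limited form. As written, the plan leaves unmanaged uterine contractions out of the AE data in both arms, and no other section recovers them. The frequency-and-intensity endpoint will therefore under-count an effect that the protocol itself attributes to merotocin. Its total frequency and full intensity distribution, including moderate events left unmanaged, cannot be estimated.

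The size is unknown. If the managed share is equal in both arms, the recorded risk difference is the true one multiplied by that share. The figures above rest on assumed rates and shares and show only this scaling. If the share differed between arms, the recorded ratio would also move, and the documents do not say in which direction. The change is worth making because it is cheap and keeps the subset the sponsor wanted.

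**What to change.** Reconcile Sections 8.1 and 8.3.1 through data recording alone:

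1. Record uterine contraction, spasm or cramping reported by the woman as an AE in both arms from informed consent, with intensity. Starting at consent matters: Sections 8.1 and 8.2.2 need a pre-dose state to separate new or worsened events from ongoing physiological ones. A start at first dose could make every ongoing contraction look treatment-emergent.
2. Add a yes/no e-CRF flag for active management, and have the sponsor define that term for the flag.
3. Count an event as treatment-emergent only if it is new or worse after the first dose, in line with Section 8.1.
4. Tabulate by arm both all treatment-emergent events and the flagged subset, each by intensity.

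The cost is a protocol amendment, one e-CRF flag with its definition, some site training, and more mild AE entries in both arms. If women have already been enrolled under the current rule, their unmanaged events may not be recoverable, so the tables should separate the two recording periods.

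If the rule is kept, the SAP and the clinical trial report should state that contraction rates cover managed events only, and Section 8.3.1 should still define active management and say whether spasm and cramping are covered.

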8.4 Morbidity Events of Special Interest for Infants

Infants' morbidity events of special interest are events of special interest because there is support or indications in the literature that their incidences and severities are associated with the degree to which premature infants are fed with mother's milk or inversely with formula based on cow-milk. The incidences of these events are therefore included in the trial design as a post-trial exploratory endpoint. These morbidities are not identified as safety parameters in the sense that there is any rationale why merotocin should have a causative effect upon them. The following infant events are regarded as morbidity events of special interest and will be followed until they are resolved or until the medical condition is stable. Additional information on NEC, intra-ventricular hemorrhage, BPD, RDS, late-onset sepsis, ROP, and hemodynamically significant patent *ductus arteriosus* will be collected in the e-CRF.

8.5 Serious Adverse Events

8.5.1 Serious Adverse Event Definition

Serious Adverse Events (SAEs) during the Trial

An event is defined a SAE if it:	Guidance
Results in death	Any event resulting in a fatal outcome must be fully documented and reported, including deaths occurring within 4 weeks after the treatment ends and irrespective of the causal relationship to the IMP. The death of a subject enrolled in a trial is per se not an event but an outcome.
Is life threatening	The term life threatening refers to an AE in which the subject was at immediate risk of death at the time of the event. It does not refer to an event that may have caused death if it were more severe.
Requires in-patient hospitalization or prolongation of existing hospitalization	The term hospitalization means that the subject was admitted to hospital or that existing hospitalization was extended as a result of an event. Hospitalization describes a period of at least 24 hours. Overnight stay for observation, stay at emergency room or treatment on an outpatient basis do not constitute a hospitalization. However, medical judgement must always be exercised and when in doubt the case should be considered serious (i.e., if case fulfils the criterion for a medically important event). Hospitalizations for administrative or social purposes do not constitute an SAE. Hospital admissions and/or surgical operations planned before trial inclusion are not considered AEs, if the illness or disease existed before the subject was enrolled in the trial, provided that the condition did not deteriorate during the trial.
Results in persistent or significant disability/incapacity	Disability/incapacity means a substantial disruption of a person's ability to conduct normal life functions. In doubt, the decision should be left to medical judgement by the investigator.
Is a congenital anomaly/birth defect	Congenital anomaly/birth defect observed in any offspring of the subject conceived during treatment with the IMP.
Is an important medical event	Medical and scientific judgment should be exercised in deciding whether other situations should be considered serious such as important medical events that might not be immediately life-threatening or result in death or hospitalization but might jeopardize the patient or might require intervention to prevent one of the other outcomes listed in the definition above. Examples of such events are intensive treatment in an emergency room or at home for allergic bronchospasm, blood dyscrasias or convulsions that do not result in hospitalization, or development of drug dependency or drug abuse.

